12.9.4. Statistical Analysis of Pharmacokinetic Data

For each individual relative bioavailability comparison the ratios of C_{max}, AUC_{0-t} and AUC will be calculated for Test:Reference using log transformed data.

The following comparisons of relative bioavailability (AUC, AUC_{0-t} and C_{max}) of verinurad will be performed:

- Treatment 2 versus 1 i.e., “A capsule, fasted” versus “ER8 capsule, fasted”
- Treatment 4 versus 1 i.e., “B capsule, fasted” versus “ER8 capsule, fasted”
- Treatment 3 versus 1 i.e., “A capsule, fed” versus “ER8 capsule, fasted”
- Treatment 5 versus 1 i.e., “B capsule, fed” versus “ER8 capsule, fasted”
- Treatment 4 versus 2 i.e., “B capsule, fasted” versus “A capsule, fasted”
- Treatment 5 versus 3 i.e., “B capsule, fed” versus “A capsule, fed”
- Treatment 3 versus 2 i.e., “A capsule, fed” versus “A capsule, fasted”
- Treatment 5 versus 4 i.e., “B capsule, fed” versus “B capsule, fasted”

Analyses will be performed using a linear fixed-effects analysis of variance model using the natural logarithm of AUC, AUC_{0-t} and C_{max} as the response variables, sequence, period and treatment as fixed effects, volunteer nested within sequence as a random effect. Transformed back from the logarithmic scale, geometric means together with confidence intervals (CIs) (2-sided 95%) for AUC, AUC_{0-t} and C_{max} will be estimated and presented. Also, ratios of geometric means together with CIs (2-sided 90%) will be estimated and presented.

12.10. Analysis of Safety Data

Safety data (scheduled and unscheduled) will be presented in the data listings. Continuous variables will be summarized using descriptive statistics (n, mean, SD, minimum, median, maximum) by treatment. Categorical variables will be summarized in frequency tables (frequency and proportion) by treatment. The analysis of the safety variables will be based on the safety analysis set.

Adverse events will be summarized by Preferred Term and SOC using MedDRA vocabulary. Furthermore, listings of SAEs and AEs that led to withdrawal of the IMP and/or from the study will be made and the number of subjects who had any AE, SAEs, AEs that led to the withdrawal, and AEs with severe intensity will be summarized. Adverse events that occur before dosing will be reported separately.

Tabulations and listings of data for vital signs, clinical laboratory tests and ECGs will be presented. Any new or aggravated clinically relevant abnormal medical physical examination finding compared to the baseline assessment will be reported as an AE. Data will be summarized for the observed values at each scheduled assessment, together with the corresponding changes (and/or percentage change) from the baseline when baseline is defined.

Clinical laboratory data will be reported in the units provided by the clinical laboratory for the Safety Review Committee meeting, and in Système International units in the CSR.

Out-of-range values for safety laboratory, vital signs and ECGs will be flagged in individual listings as well as summarized descriptively using agreed standard reference ranges and/or extended reference ranges (e.g., AZ, program, or laboratory ranges).

12.10.1. Adverse Events

All AEs will be coded using MedDRA vocabulary and will be listed for each subject. A treatment-emergent adverse event is defined as an AE with onset (start date/time) after the first dose of verinurad in Treatment Period 1.

Adverse events will be assigned to a treatment based on the start date/time of the AE in relation to dosing in that period; for tabulation purposes the AE will then be assigned to the treatment received in the respective treatment period as follows:

- Screening: all SAEs with start date/time prior to dosing in Treatment Period 1.
- Treatment Period 1: AEs with start date/time at the time of or after dosing in Treatment Period 1 until the time of dosing in Treatment Period 2.
- Treatment Period 2: AEs with start date/time at the time of or after dosing in Treatment Period 2 until the time of dosing in Treatment period 3.
- Treatment Period 3: AEs with start date/time at the time of or after dosing in Treatment Period 3 until the time of dosing in Treatment Period 4.
- Treatment Period 4: AEs with start date/time at the time of or after dosing in Treatment Period 4 until the time of dosing in Treatment Period 5.
- Treatment Period 5: AEs with start date/time at the time of or after dosing in Treatment Period 5 until the Follow-up Visit.

Adverse events with missing start dates/times will be handled as follows:

- If the start date is completely missing but the end date is known and shows that the AE ended on or after the first dose date, then the start date will be imputed as the first day of dosing; if the end date is known and shows that the AE ended before the first dose date, then the screening date will be used for the start date. If the end date is non-informative (i.e., is missing or does not contain enough information), the start date will be imputed as the first date of dosing;
- If only the start day is missing the day will be imputed as the first day on which a dose was given in that month unless the end date is known and shows that the AE ended before a dose was given in that month; in which case the date will be imputed as 01. If the end date is non-informative (i.e., is missing or does not contain enough information), the start

- date will be imputed as the first date of dosing in the known month. If the month is not a dosing month the date will be imputed as 01;
- If the start day and month are missing the date will be imputed as the first day of dosing in the known year unless the end date is known and shows that the AE ended before a dose was given in that year; in which case the start day and month will be imputed as 01Jan or with the date of screening if this is later. If the end date is non-informative (i.e., is missing or does not contain enough information), the start date will be imputed as the first date of dosing in the known year. If the year is not a year of dosing then the date will be imputed as 01Jan or with the date of screening if this is later.
 - Missing times will be imputed as 00:00 h or with the time of dosing for events starting on a dosing day.

Adverse events will be summarized by treatment (where treatments will be pooled across treatment periods) and overall for all subjects, including tabulations by causality and severity (mild, moderate and severe). All tabulations will be presented by SOC and Preferred Term. Furthermore, separate listings of SAEs, AEs that led to discontinuation of the IMP, AEs that led to withdraw from the study and AEs that led to death will be presented.

The following information will be included in the listings: verbatim term, SOC, PT and start date/time, end date/time, time from last dose, causality, action taken, whether the AE was classified as serious and the outcome.

All tabulations will include the number and percentage of subjects. In addition, a separate tabulation will be presented showing the number of events by treatment and PT.

Finally, an overview of all AEs will be presented, separately for the number and percentage of subjects and the number of events. This will include categories for any AE, AEs with the outcome of death, SAEs and discontinuations of IMP/withdrawals from the study.

12.10.2. Vital Signs

The results of the vital signs measurements will be listed by subject and time point including the date/time of the assessment, changes from baseline and repeat/unscheduled measurements. The baseline for vital signs measurements will be the pre-dose assessment on Day 1 in each treatment period. Descriptive statistics will be presented by treatment and time point for both observed values and changes from baseline.

12.10.3. Resting 12-lead Electrocardiogram

12-Lead ECG results will be listed for each subject.

12.10.4. Physical Examination

The baseline/screening results of the physical examination will be documented in medical history for each subject.

Any new or aggravated clinically relevant abnormal medical physical examination finding compared to the baseline assessment will be reported as an AE.

The results of the physical examination will be listed by body system for each subject.

12.10.5. Laboratory Assessments

Haematology and clinical chemistry values will be listed by subject and time point including changes from baseline and repeat/unscheduled measurements. Summary tabulations including absolute value and changes from baseline will be presented by treatment and time point for the safety analysis set. The baseline for the measurements will be the Day -1 assessment performed prior to dosing in each treatment period. Shift tables, by treatment, will also be presented.

The listings will include the following information: test name, date of measurement, reference range, result and flags for any measurements that are outside the reference range (e.g., AstraZeneca, program, or laboratory ranges). Clinical laboratory data will be reported in System International units in the CSR.

Additional listings will be presented for the following:

- Urinalysis (macroscopic and microscopic, if applicable).
- Pregnancy testing (including FSH).
- The results of viral serology and the drugs of abuse and alcohol screen will not be listed in the CSR.

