5.3.3. Study Flow Chart and Schedule of Assessments

The flow of events is illustrated in Figure 5-1 for all treatments, depending on the subject's assigned randomization (refer to Section 9.9.2).

The Schedule of Assessments displaying assessments/tasks and time points are presented in Table 5-2.

Figure 5-1 Study Flow Chart

Treatment 1: 1 x 12 mg verinurad ER8 capsule formulation, fasted.;
 Treatment 2: 2 x 6 mg verinurad A capsule formulation, fasted.
 Treatment 3: 2 x 6 mg verinurad A capsule formulation, fed.
 Treatment 4: 2 x 6 mg verinurad B capsule formulation, fasted.
 Treatment 5: 2 x 6 mg verinurad B capsule formulation, fed

^a Randomization on Day -1 of Treatment Period 1.

^b Residential period. Admission to Clinical Unit on Day -1, discharge from Clinical Unit on Day 4

Table 5-2 Schedule of Assessments

Visit	Screening	Treatment Periods 1, 2, 3, 4 and 5		Follow-up Visit	Corresponding Section in Protocol
		Day -1	Day 1 to 4		
Study Day	Day -28 to -2			7 to 14 days post-final dose	
Inclusion/exclusion criteria ¹	X	X			Section 7.1
Demographic data	X				Section 12.7
Medical history	X				Section 12.8
Urinary drug/alcohol screen	X	X			Section 10.3.5.6
Serology	X				Section 10.3.5.5
Informed consent	X				Section 3.5
Randomization		X ²			
Study Residency:					
Check-in		X (in the morning)			Section 5.3.2
Check-out			Day 4 (after 72 h post-dose assessments)		Section 5.3.2
Non-residential visit	X			X	Section 5.3.2
Verinurad Administration:			Day 1 (0 h)		Section 5.3.2 and Section 9.6
Safety and Tolerability:					
Adverse event questioning ³	X	X	Spontaneous plus Day 1: pre-dose, 3 and 12 h post-dose Day 2: 24 h post-dose Day 3: 48 h post dose Day 4: 72 h post-dose	X	Section 10.3.1

Visit	Screening	Treatment Periods 1, 2, 3, 4 and 5		Follow-up Visit	Corresponding Section in Protocol
		2, 3, 4, 5 and 6	Day 1 to 4		
Study Day	Day -28 to -2	Day -1	Day 1 to 4	7 to 14 days post-final dose	
Prior and concomitant medications questioning	X	X	X	X	Section 9.7
Blood pressure and pulse rate (supine)	X	X	Day 1: Pre-dose Day 4: 72 h post-dose	X	Section 10.3.2
Safety 12-lead Electrocardiograms	X			X	Section 10.3.3
Clinical laboratory evaluations ⁴	X	X		X	Section 10.3.5.1, Section 10.3.5.2 and Section 10.3.5.3
Physical examination ⁵	X	X (brief)	Day 4: 72 h post-dose (brief)	X (brief)	Section 10.3.5.4
Body weight and height, BMI	X				
Pregnancy test ⁶	X	X		X	
Pharmacokinetics					

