Pharmacokinetic sampling for verinurad			Day 1: Pre-dose, 0.5, 1, 1.5, 2, 3, 4, 5, 6, 8, 10 and 12 h post-dose Day 2: 24 and 36 h post-dose Day 3: 48 h post-dose Day 4: 72 h post-dose		Section 10.2

BMI = Body mass index.

- To be reconfirmed on Day -1 of each treatment period.
 - Randomization to take place with admission to the unit on Day -1 of Treatment Period 1.
 - Adverse Events will be collected from the start of randomization throughout the treatment periods up to and including the Follow-up Visit. Serious adverse events will be recorded from the time of informed consent.
 - Blood (clinical chemistry and haematology) and urine (urinalysis) sample collection. Fasting samples: collected in the morning of admission following an overnight fast at home with no breakfast before admission. Admission to take place in the morning to ensure fasted samples.
- Footnotes continues on next page*

- ⁵ A complete physical examination should include general appearance, respiratory, cardiovascular, abdomen, skin, head, and neck (including ears, eyes, nose and throat), lymph nodes, thyroid, musculoskeletal and neurological systems.
A brief physical examination should include general appearance, skin, abdomen, cardiovascular system and respiratory; and any organ systems pertinent to the patient's signs, symptoms or AEs.
Full physical examination at screening and brief assessment at: admission to the first treatment period, 72 hours post each dose and at the Follow-up Visit.
- ⁶ Serum pregnancy test at screening, urine pregnancy test at admission to each treatment period and the Follow-up Visit.

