5.3.4. Total Blood Volume

The approximate total amount of blood to be collected from each subject in this study, excluding repeat samples, is summarized in [Table 5-3](#).

Table 5-3 Total Blood Volume

	Volume per Sample	Number of Samples	Total
Clinical Laboratory:			
Haematology	2.7 mL	7	18.9 mL
Clinical chemistry ^a	7.5 mL	7	52.5 mL
Pharmacokinetics:			
Verinurad sampling	2 mL	80	160 mL
Total			231.4 mL

^a When applicable, serology, serum pregnancy (females only) and follicle stimulating hormone analyses will be performed on the sample collected for clinical chemistry analyses.

Repeat blood samples may be collected for safety reasons. The maximum volume to be drawn from each subject must not exceed 500 mL.

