13.1.3. Other Significant Adverse Events

During the evaluation of the AE data, an AstraZeneca medically qualified expert will review the list of AEs that were not reported as SAEs. Based on the expert's judgment, significant AEs of particular clinical importance may, after consultation with the Global Safety Physician, be considered Other significant adverse events (OAEs) and reported as such in the CSR. A similar review of other data from laboratory tests, vital signs, ECGs and other safety assessments will be performed for identification of OAEs.

Examples of these are marked haematological and other laboratory abnormalities, and certain events that lead to intervention (other than those already classified as serious), dose reduction or significant additional treatment.

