13.2.6. Adverse Events Based on Examinations and Tests

The results from protocol-mandated laboratory tests, vital signs, ECGs and other safety assessments will be summarized in the CSR.

Deterioration as compared to baseline in protocol-mandated laboratory values, vital signs, ECGs and other safety assessments should therefore be reported as AEs if they constitute a clinically significant deterioration from baseline.

If deterioration in a laboratory value or vital sign is associated with clinical signs and symptoms, the sign or symptom will be reported as an AE and the associated laboratory result or vital sign will be considered as additional information.

Wherever possible the reporting PI should use the clinical, rather than the laboratory term (e.g., anaemia versus low Hb value).

In the absence of clinical signs or symptoms, clinically relevant deteriorations in non-mandated parameters should be reported as AE(s).

Any new or aggravated clinically relevant abnormal medical finding at a physical examination as compared with the baseline assessment will be reported as an AE.

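### The laboratory baseline resets at every Day -1 although no chemistry is scheduled on Days 1-4, so the by-treatment change and shift tables are thin and can absorb a carried-over creatinine rise (minor)

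*Protocol*

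**What the plan says.** Protocol Section 12.10.5 plans by-treatment summaries of laboratory values and of their changes from baseline. It fixes the baseline as follows: "The baseline for the measurements will be the Day -1 assessment performed prior to dosing in each treatment period". It adds: "Shift tables, by treatment, will also be presented".

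The sampling schedule is in Table 5-2 (Section 5.3.3). The row "Clinical laboratory evaluations" is marked at screening, Day -1 and follow-up, and its Day 1 to 4 cell is empty. Footnote 4 gives the timing within a period: "Fasting samples: collected in the morning of admission following an overnight fast at home with no breakfast before admission". In Table 5-3 (Section 5.3.4) the row "Clinical chemistry" shows 7 samples per subject.

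For adverse events, Section 12.10.1 does assign the interval between doses to the earlier treatment. Treatment Period 1, for example, takes "AEs with start date/time at the time of or after dosing in Treatment Period 1 until the time of dosing in Treatment Period 2". No visible text gives such a rule for laboratory values. Section 12.1 plans no separate SAP, only an abbreviated one if analyses change.

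**The concern.** A change from baseline by treatment needs a value after that treatment's dose. Vital signs also have a per-period baseline (Section 12.10.2), but Table 5-2 gives them a 72 h reading in every period. Laboratory tests have the same baseline structure without a reading inside the period.

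Two consequences follow. First, on a literal reading the change and shift tables are nearly empty. Second, each reset hides whatever rise a subject carries forward into the next period.

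Safety and tolerability is a secondary objective. Section 5.5 names creatinine elevation relative to baseline as the main concern of giving verinurad without a xanthine oxidase inhibitor. The reporting tables should therefore be able to show that quantity against a value taken before any exposure.

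**Working it through.** **Reproducing the schedule.** Screening 1 + Day -1 visits 5 + follow-up 1 = 7 samples, as in Table 5-3. The volumes agree: 7 x 7.5 mL = 52.5 mL chemistry and 7 x 2.7 mL = 18.9 mL haematology. No scheduled chemistry falls on Days 1-4.

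**Literal count for completers.**
- Inputs: 25 subjects, 5 per sequence (Section 7.3); sequences 12345, 23451, 51234, 34512 and 45123 (Section 9.9.2).
- Dosings: 25 x 5 = 125.
- In Periods 1-4 the only scheduled sample after the dose is the next Day -1, which is the next period's baseline. Only follow-up against the Period 5 Day -1 remains, one change per completer: 25/125 = 20%.
- The Period 5 treatments by sequence are 5, 1, 4, 2 and 3, each with 5 subjects, so n = 5 per treatment.
- With 20 completers, 4 per sequence (the planned minimum): 20/100 = 20%, n = 4 per treatment.

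**Subjects stopped at a later Day -1.** The baseline is defined as an assessment before dosing. If no dose follows, that Day -1 value is not a baseline. It is a post-dose value of the preceding treatment, beside follow-up. A sustained rise that stops dosing therefore stays visible.

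**Subjects who continue.** Section 16.4.2 allows dosing to go on after two successive values below 1.5-fold, and a rise that never reaches 1.5-fold stops nothing. Two illustrations with assumed creatinine values:
- *Literal reading.* 0.80 mg/dL up to the Period 4 Day -1, 1.12 at the Period 5 Day -1 (1.12/0.80 = 1.40; +0.32), 0.80 at follow-up. The only tabulated change is 0.80 - 1.12 = -0.32 mg/dL (-0.32/1.12 = -29%), a fall.
- *Next Day -1 also counted as post-dose.* 0.80, 0.95 and 1.10 at the Day -1 visits of Periods 1, 2 and 3, then 1.10 throughout. The tabulated ratios are 0.95/0.80 = 1.19, 1.10/0.95 = 1.16, then 1.00. The rise from before the first dose is 1.10/0.80 = 1.375 (+0.30 mg/dL), and no change table shows it.

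**What range flags miss.** A 1.5-fold rise stays within range if the starting value is at most 1/1.5 = 0.67 x ULN. A 1.25-fold rise does so if it is at most 1/1.25 = 0.80 x ULN.

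**How many such rises.** The pooled Phase 1 rates in Section 5.2.3.1, applied to 25 subjects, give:
- at least 1.25 x baseline: 25 x 0.137 = 3.4 subjects;
- at least 0.3 mg/dL above baseline: 25 x 0.068 = 1.7;
- at least 1.5 x baseline: 25 x 0.017 = 0.4.

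These are best taken as ceilings. With at least 5 days between doses, the next Day -1 is at least about 5 - 1 = 4 days = 96 h after dosing, which is 96/13 = 7.4 half-lives at the 13 h of Section 5.2.3.2. Section 5.5 describes the elevations as mainly transient. The plausible range runs from 0 to the counts above.

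**After the fix.** Four later Day -1 values + follow-up = 5 post-dose values per completer; 25 x 5 = 125, n = 25 per treatment.

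**The case against.** One sample can be the baseline of its own period and the post-dose value of the one before. Section 12.10.5 does not forbid this, the adverse event rule in Section 12.10.1 points that way, and the redacted part of Section 12.2 may say so. That stands: n = 5 per treatment is the literal reading of the visible text, not a certainty. It does not remove the absorption, because each change would still start from a reset value. A per-period baseline is otherwise a defensible crossover choice.

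Much is also covered elsewhere:
- Under Section 13.2.6, worsened laboratory values "should therefore be reported as AEs if they constitute a clinically significant deterioration from baseline".
- Section 12.10 flags and summarises out-of-range values.
- Section 13.1.3 adds expert review: "A similar review of other data from laboratory tests, vital signs, ECGs and other safety assessments will be performed for identification of OAEs".
- Absolute values are tabulated, and all values, including repeats, are listed.
- Sections 8.1 and 16.4.2 handle rises around 1.5-fold subject by subject.

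This also stands. It leaves only in-range relative rises not judged clinically significant.

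A reader might infer that a creatinine rise large enough to stop dosing would vanish from the tables, or that no subject can contribute more than one scheduled change. Neither follows, since a Day -1 value with no later dose is not a baseline. Nor do the documents support the inference that stopping decisions are weakened: Section 8.1 refers to the value before treatment, and nothing ties it to the reporting baseline of Section 12.10.5.

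**Conclusion.** The point holds as a minor one about descriptive safety reporting. The stated baseline rule does not fit the stated schedule. For 25 completers, the literal result is 25 of 125 dosings in the change and shift tables, 5 per treatment. In subjects who continue dosing, a rise carried to a later Day -1 is absorbed on either reading of how Day -1 values are assigned.

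The counts assume full completion, scheduled samples only, and no contrary rule in the redacted text of Section 12.2. The number of rises actually hidden may be zero. The pharmacokinetic analysis, the randomisation and individual stopping decisions are not affected.

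**What to change.** Make two additions to Section 12.10.5.

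1. An assignment rule:

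> For the change-from-baseline and shift tables, the Day -1 value of the next period (Periods 2-5) is also the post-dose value of the preceding treatment, and follow-up is the post-dose value of the last treatment received.

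2. One creatinine table with a listing flag:

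> The baseline is the last value before the first dose in Treatment Period 1. The table gives the number and percentage of subjects with creatinine at least 1.5 x baseline and, as supportive counts, at least 1.25 x baseline and at least 0.3 mg/dL (or its SI equivalent) above baseline, primarily overall and secondarily by most recent treatment. The counts are a lower bound, because transient rises can be missed.

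The first addition brings the tables to n = 25 per treatment for completers. In the first illustration, it shows +0.32 mg/dL under the Period 4 treatment beside the fall under Period 5. The second addition shows the rise from before any exposure.

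The cost is one sentence, one table and one flag on data already collected, with no new sample or visit. A persisting rise recurs under each later treatment, so the overall count should be read first. A low count does not exclude short-lived rises, because the sampling schedule is unchanged.
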